- 2) Dexamethasone Sodium Phosphate Injection 10mg/ml. APP Pharmaceuticals LLC, Schaumburg, Ill. NDC Code: 63323-506-01, 63323-516-10
- 3) McKesson ID 2070274 Adrenalin Chl. Inj. 1mg/ml 1ML25 epinephrine NDC 2023015925.

For each nerve block, the epinephrine will be added to the bupivacaine and dexamethasone in a sterile fashion and used within 24 hours of the epinephrine being added. Otherwise, the solution will be discarded. All procedures will be performed under a sterile technique including the use of a chlorohexidine prep of the skin, sterile gloves, a sterile ultrasound probe cover with sterile ultrasound gel, and a cap and a mask. A 21-gauge 90 mm Arrow StimuQuick, stimulating needle (Teleflex, USA) will be directed under real-time ultrasound guidance into the adductor canal. The local anesthetic solutions will be injected incrementally in 5 mL aliquot to a total volume of 20 mL to surround the saphenous nerve.

Study subjects will receive either a spinal anesthetic with propofol sedation (25–100 µg/ kg/min) or a general anesthetic for their surgical procedure. Patients will undergo their surgery and be brought to the post-anesthesia recovery unit (PACU). The patient will remain in the PACU until resolution of the spinal from the non-operative side.

These participants will be observed overnight and will be evaluated every two hours with pin-prick (performed with a 25 gauge Whitacre needle in the cutaneous distribution of the saphenous nerve on the medial aspect of the blocked leg) to monitor for the duration of the sensory block until sensation is fully returned. This testing will be performed by research assistants. If the duration of their sensory block should last past admission, the patients will be educated during their hospitalization assessments on how to assess their own block every two hours at home using a safety pin. Research assistants will continue to call patient's every two to three hours

during this time until block resolution occurs to instruct the participants and answer any questions. During their stay, their pain management will be managed by the Acute Pain Service. They will also be asked about their pain using the visual analog scale, post operative nausea and vomiting rates, and opioid consumption will be followed. Comparisons will then be made between the three groups and the data will be analyzed.

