### **Analytical Plan:**

#### **Power / Sample Size:**

The primary sample size consideration is the comparison between the 1 mg and 4 mg of dexamethasone arms, where the goal is to demonstrate that the duration of PNB is clinically equivalent between the two arms. Note that this hypothesis, statistically, is reversed from what is usually tested in a superiority trial. We have assumed that clinically equivalent means that the average duration of PNB for 1 mg of dexamethasone is  $\pm$  4 hours from the average duration for 4 mg. In other words, the difference in mean duration for the two dexamethasone arms (D) falls on the interval (-4 hrs to 4 hrs). Statistically, a successful trial would then reject the null hypothesis  $H_0: D < -4$  hrs or  $D > 4$  hrs. The previously mentioned Toronto study [5] reported a mean duration of analgesia of 25 hours (95% CI: 19.5-27.4) for 25 patients randomized to 8 mg of perineural dexamethasone. While the test of clinical equivalence will be based on the boundary of  $\pm$  4 hours, in order to permit power calculations one has to make an assumption about the true difference in mean duration. The most liberal assumption is that there is absolutely no difference in mean duration between the arms (i.e.  $D=0$ ). To be more conservative, we have assumed that the true mean duration for 4 mg of dexamethasone is  $\pm$  1.5 hours from the true mean duration for 8 mg. This assumption implies that a study of 50 participants per group (allowing for 10% drop-out) will have  $>80\%$  power to declare the two doses as clinically equivalent. Note that this calculation assumes a type 1 error rate of  $0.05/3 = 0.1667$ , as the study has three planned comparisons (two dexamethasone doses versus each other, and then both versus the placebo control). We plan to recruit a reduced sample size for the placebo control arm, as the difference in duration of PNB when compared to both dexamethasone arms is expected to be large. Provided the average duration of PNB is at least 5 hours longer for either dexamethasone arm, we will have  $>90\%$  power recruiting only 15 subjects (allowing for 10% drop-out) to the placebo control arm. Note that the Toronto study [5] reported an average improvement of 11.8 hours when comparing 8 mg of perineural dexamethasone to their control arm.

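### A flat 0.05/3 per comparison leaves alpha unused and no analysis rule is stated; prespecifying Holm would raise equivalence power (about 80% to 91% at an assumed SD of 3.95 h) at no cost in patients

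*Combined protocol and SAP*

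**What the plan says.** The Power / Sample Size section makes equivalence of 1 mg and 4 mg the main sizing question, to be shown if "the difference in mean duration for the two dexamethasone arms (D) falls on the interval (-4 hrs to 4 hrs". It sizes that test at 0.05 divided by three, "as the study has three planned comparisons (two dexamethasone doses versus each other, and then both versus the placebo control". The quotient is printed as 0.1667, but 0.05/3 is 0.0167.

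The control arm is kept small because "the difference in duration of PNB when compared to both dexamethasone arms is expected to be large". The calculation requires a gain of at least 5 h over control and cites 11.8 h for 8 mg in an earlier trial.

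The Analytical Plan contains nothing beyond this power section. The only other analysis text, at the end of Interventions and Interactions, is "Comparisons will then be made between the three groups and the data will be analyzed". No stepwise, ordered or gatekeeping rule appears anywhere, and no SD is stated.

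**The concern.** A Bonferroni split controls the family-wise error, so this is a question of efficiency and of a missing rule, not of validity. The two comparisons expected to succeed easily each hold a third of the alpha, and the demanding one runs at 0.0167. Holm passes alpha on: once both control comparisons are rejected, the equivalence test is run at the full 0.05.

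If the analysis follows the sizing assumption, the trial gives up power on its main claim for no gain in error control. If it does not, the multiplicity method could be chosen after the results are seen.

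**Working it through.** **Inputs from the plan.** Margin ±4 h; 50 per dexamethasone arm less 10%, so 45 evaluable; control arm 15 less 10%, so 13.5; per-comparison alpha 0.05/3.

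**Assumptions.** The true difference between 1 mg and 4 mg is taken as 1.5 h, although the text places 4 mg at ± "1.5 hours from the true mean duration for 8 mg". Equivalence is tested by two one-sided tests (TOST), each at 0.05/3; the control comparisons are two-sided.

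**SD.** The only information on spread is that the cited trial "reported a mean duration of analgesia of 25 hours (95% CI: 19.5-27.4) for 25 patients randomized to 8 mg of perineural dexamethasone".
- Half-width: (27.4 − 19.5)/2 = 3.95 h.
- Implied SD: 3.95 × √25 / 2.064 = 9.57 h (t), or 3.95 × 5 / 1.96 = 10.08 h (z). This treats the interval as symmetric, which it is not: it runs 5.5 h below and 2.4 h above the reported mean of 25.
- The largest SD giving 80% power with 45 per arm at 0.05/3 is 3.94 h (t-based), so 3.95 h is used as the value consistent with the plan's power claim. It coincides with the CI half-width. Whether the plan used that figure is an inference.

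**Reproducing the plan.** n per arm = 2·SD²·(z_α + z_β)² / (4 − 1.5)². At SD 3.95 h this is 2 × 15.60 × (2.128 + 0.842)² / 6.25 = 44.0, so 45, and 45/0.9 = 50 per arm, as stated.

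Power = Φ(2.5/SE − z_α) + Φ(5.5/SE − z_α) − 1, with SE = 3.95 × √(2/45) = 0.833. At 0.0167 this is Φ(3.002 − 2.128) = 80.9% (79.8% with t), the second term being essentially 1. The 5 h control comparison then has 94.8% to 95.9% power with 13 to 14 controls, in line with the stated 90%. Halving alpha again, to 0.0083 per side, gives only 72.8% for equivalence, so the one-sided reading is the one that fits.

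**Ceiling under Holm.** At 0.05: Φ(3.002 − 1.645) = 91.3% (90.9% with t).

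**Simulation of all three arms** (45/45/13.5, or 13 controls in a check; pooled variance; true difference 1.5 h). Gains are hours over control for 1 mg / 4 mg:

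| SD (h) | Flat 0.05/3 | Holm, gains 10.3/11.8 | Holm, gains 5/6.5 |
|---|---|---|---|
| 3.5 | 89% | 96% | not run |
| 3.95 | 80% | 91% | 90% |
| 5 | 58% | 76% | 73% |
| 9.57 | 0.6% | 18% | 7% |
| 10.08 | 0.1% | 13% | 4% |

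No rejection made by the flat split was lost under Holm in any simulated trial.

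**Error control.** With a true difference of exactly 4 h, gains of 7.8/11.8 h and SD 3.95 h, false equivalence is 1.7% under the flat split and 5.0% under Holm. Across the null configurations tried, Holm's family-wise error was 4.1% to 5.0%.

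**In patients.** Evaluable n per arm for 80% power at SD 3.95 h (t-based) is 46 at 0.0167 and 32 at 0.05. With 45 per arm, the largest SD that still gives 80% is 3.94 h at 0.0167 and 4.73 h at 0.05.

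**The case against.** - **Bonferroni is valid, and the text does not commit the analysis to it.** The wording is "Note that this calculation assumes a type 1 error rate of", which is a sizing input. Sizing at 0.05/3 and analysing with Holm would be compatible. This stands in part: the alpha is lost only if the analysis also uses the flat split. What remains is that no analysis rule is stated.
- **The 80% starting point is back-solved.** The SD of 3.95 h was chosen because it returns the plan's power. At the SD implied by the quoted interval, neither rule makes the equivalence test informative. This stands, and the SD is the larger problem. Holm still has higher power at every SD tried.
- **The calculation might really have been run at 0.1667.** In that case 80% power with 45 per arm corresponds to an SD of about 6.5 h, where power is 34% at 0.0167 and 48% to 56% under Holm. A misprint is the likelier reading, because 3.95 h returns exactly 50 per arm.
- **Holm allows equivalence of two ineffective doses.** This is true, and equally so for the flat split: with no gain for either dose and SD 3.95 h, both declare equivalence in about 99% of trials. A fixed sequence blocks such claims at almost the same power (90.9% at the larger gains; 89% against 90% for Holm at gains of 5/6.5 h). Choosing it is a legitimate alternative.
- **Interval reporting becomes less tidy.** The level of the interval for the difference depends on the step reached, and the joint coverage of Bonferroni intervals is lost. This is a small cost.

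**Conclusion.** The point holds as an improvement to consider, not as an error of validity. The plan's only multiplicity statement is a flat 0.05/3 used for sizing, misprinted as 0.1667, and there is no rule for the analysis. Holm controls the same 5% family-wise error and never rejects less. Given a true difference of 1.5 h and clear gains over control, it adds about 11 percentage points of equivalence power at an SD of 3.95 h and about 18 at 5 h. These gains rest on an SD that the plan does not state. At 9.6 to 10.1 h, equivalence power stays below 20% under either rule.

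**What to change.** In the Analytical Plan, prespecify Holm over the three p-values as the analysis rule. The equivalence p-value is the larger of the two one-sided p-values. The ordered p-values are compared with 0.0167, 0.025 and 0.05 from the smallest upward, stopping at the first failure. Report the confidence interval for the difference between the two doses at the level matching the step reached: 96.7%, 95% or 90%. Correct 0.1667 to 0.0167. State and justify the SD separately.

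If the sponsor also wants no equivalence claim unless 1 mg beats control, use instead a fixed sequence: 4 mg against control, 1 mg against control, then equivalence, each at 0.05. Its cost is that no later claim is possible once an earlier step fails. Holm alone does not give that protection.

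The change takes one or two sentences, fixed before unblinding, with no extra patients or data. Compared with the flat split, Holm loses neither power nor family-wise error control; the price is an interval whose level depends on the step reached.

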### **Human Subjects Protection:**

**Subject Recruitment Methods:**

Potential study participants will be identified based on the posting of their surgical procedure as undergoing elective robotic medial and/or patellofemoral MAKO partial knee arthroplasty. On the day of surgery all patients undergoing this surgical procedure normally come through the regional anesthesia area of surgical services to receive further anesthetic evaluation, education, and potential regional anesthesia procedures. Once they have been consented by the regional anesthesia team for a peripheral nerve block, all patients, regardless of gender, race or age, who qualify for the study based on inclusion and exclusion criteria will be formally asked to participate in the study at this time. All patient information will be kept confidential both during recruitment and throughout the duration of the study.

**Informed Consent:**

Written informed consent will be obtained from each subject. It can be obtained by any physician listed as part of the study staff. If possible, patients scheduled for elective robotic medial and/or patellofemoral MAKO partial knee arthroplasty will be seen in the preoperative assessment clinic at North Carolina Baptist Hospital. Otherwise, as is typical for regional anesthesia techniques, the study team will meet the patient in the Regional Anesthesia and Acute Pain Management area. They will be informed of the purpose of the study along with the risks, benefits, and alternatives. Questions will be answered and consent obtained. A copy of the signed informed consent will be placed in the patient's medical record. All subjects may decline participation in the study at any time. Informed consent and all necessary study data will be obtained prior to the administration of any sedative medication.

**Confidentiality and Privacy**

Confidentiality will be protected by collecting only information needed to assess study outcomes, minimizing to the fullest extent possible the collection of any information that could directly identify subjects, and maintaining all study information in a secure manner. To help ensure subject privacy and confidentiality, only a unique study identifier will appear on the data collection form. Any collected patient identifying information corresponding to the unique study identifier will be maintained on a linkage file, stored separately from the data. The linkage file will be kept secure, with access limited to designated study personnel. Following data collection subject identifying information will be destroyed at the earliest opportunity, consistent with data validation and study design, producing an anonymous analytical data set. Data access will be limited to study staff. Data and records will be kept locked and secured, with any computer data password protected. No reference to any individual participant will appear in reports, presentations, or publications that may arise from the study.

**Data and Safety Monitoring**

The principal investigator will be responsible for the overall monitoring of the data and safety of study participants. The principal investigator will be assisted by other members of the study staff.

**Reporting of Unanticipated Problems, Adverse Events or Deviations**

Any unanticipated problems, serious and unexpected adverse events, deviations or protocol changes will be promptly reported by the principal investigator or designated member of the research team to the IRB and sponsor or appropriate government agency if appropriate.

**Appendix:**

1. Data Collection Form
2. Consent Form
3. FDA IND Acknowledge/Exemption 125810
